7.3.3 Sponsor's SAE Reporting Requirements

Sponsor/Sponsor representative is responsible for reporting relevant SAEs to the competent authority, other applicable regulatory authorities, and participating investigators, in accordance with ICH guidelines, FDA regulations, and/or local regulatory requirements.

Sponsor/sponsor representative is responsible for reporting unexpected fatal or life-threatening events associated with the use of the trial drugs to the regulatory agencies and competent authorities via telephone or fax within 7 calendar days after being notified of the event.

The Sponsor will report all related, unexpected SAEs, including non-death/non-life-threatening related unexpected SAEs associated with the use of the trial medications to the FDA by a written safety report within 15 calendar days of notification. Reporting to the IRB/IEC will be done according to institutional policy.

7.4 Recording of AE and SAE

Investigators should use correct medical terminology/concepts when recording AEs or SAEs on the SAE Report Forms and AE eCRF. Avoid colloquialisms and abbreviations. All AEs, including those that meet SAE reporting criteria, should be recorded on the AE eCRF; AEs that meet the

definition of an SAE should additionally be reported following the procedures noted in above sections.

7.4.1 Diagnosis vs. Signs and Symptoms

All AEs should be recorded individually in the patient's own words (verbatim) unless, in the opinion of the Coordinating Investigator or designated physician, the AEs constitute components of a recognized condition, disease, or syndrome. In the latter case, the condition, disease, or syndrome should be named rather than each individual sign or symptom. If a constellation of signs and/or symptoms cannot be medically characterized as a single diagnosis or syndrome at the time of reporting, each individual event should be recorded as an AE or SAE as appropriate on the relevant form(s) (SAE Report Form and/or AE eCRF). If a diagnosis is subsequently established, it should be reported as follow-up information is available. If a diagnosis is determined subsequent to the reporting of the constellation of symptoms, the signs/symptoms should be updated to reflect the diagnosis.

7.4.2 Persistent or Recurrent Adverse Events

A persistent AE is one that extends continuously, without resolution, between patient evaluation time points. Such events should only be recorded once on the SAE Report Form and/or the AE eCRF, irrespective of severity. (E.g. If a persistent AE becomes more severe or lessens in severity, it should be recorded once with highest grade of severity on a SAE Report Form and/or AE eCRF).

A recurrent AE is one that occurs and resolves between patient evaluation time points, and subsequently recurs. All recurrent events should be recorded separately on an SAE Report Form and/or AE eCRF.

7.4.3 Abnormal Laboratory Values

Any grade 3 or 4 laboratory abnormalities or any clinically significant grade 1 or 2 hematology or biochemistry laboratory value(s) should be recorded as an AE. Isolated laboratory abnormality without clinical significance should not be captured as AE if confirmed by the investigator. If an abnormal laboratory value or vital sign is associated with clinical signs and/or symptoms, the sign or symptom should be reported as an AE, and the associated laboratory value or vital sign should be considered additional information that must be collected on the relevant eCRF. If the laboratory abnormality is a sign of a disease or syndrome, only the diagnosis needs to be recorded on the SAE Report Form or AE eCRF.

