1.1.2 Summary of Clinical Evaluation

To date, Tenalisib has been evaluated in four clinical trials:

1. A Phase I Dose Escalation Study Evaluating the Safety and Efficacy of RP6530, a dual PI3K δ/γ inhibitor, in Patients with Relapsed or Refractory Hematologic Malignancies (European study: Protocol Number RP6530-1301) Status: Completed
2. A Phase I/Ib, Dose Escalation Study to Evaluate Safety and Efficacy of RP6530, a dual PI3K δ/γ inhibitor, in Patients with Relapsed or Refractory T-cell Lymphoma (US study: Protocol number RP6530-1401). Status: Recruitment completed. Study Ongoing
3. An open label, randomized, single dose, crossover study to evaluate food effects on relative bioavailability of RP6530 administered in fasting and fed conditions in healthy volunteers (Food effect study, Protocol no: RP6530-1501). Status: Completed
4. An Open label, Phase I/II study to evaluate the safety and efficacy of RP6530, a novel PI3K δ/γ dual inhibitor given in combination with an anti-PD-1 therapy, Pembrolizumab in adult patients with relapsed or refractory Classical Hodgkin's lymphoma (cHL). Status: Ongoing and currently recruiting.

- **Safety:**

In RP6530-1401 study, a total of 58 patients were treated at 200 mg BID (n=4), 400 mg BID (n=4), 800 mg BID (Fasting) (n=44) and 800 mg BID (Fed) (n=6) in both dose escalation and dose expansion cohorts. Tenalisib demonstrated acceptable safety and tolerability profile up to 800 mg BID (fasting). Tenalisib 800 mg BID (Fasting) was considered as MTD dose in patients with T-cell lymphoma. Majority of AEs include transaminitis, skin rash. Treatment related Grade ≥ 3 includes AST/ALT elevation (n=12), rash (n=4), hypophosphatemia (n=2), neutropenia (n=1), INR Increase (n=1), sepsis (n=1), pyrexia (n=1), diplopia secondary to neuropathy (n=1), drug reaction (n=1), and bacteremia (n=1). Treatment related SAE reported were pyrexia (n=1), raised INR (n=1), sepsis (n=1), diplopia secondary to neuropathy (n=1), drug reaction (n=1) and bacteremia (n=1).

- **Pharmacokinetics:**

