3 TRIAL DESIGN

3.1 Trial End Points

3.1.1 Primary Endpoint

- **Safety:**
Adverse Event (AE), Grade 3/ 4 AEs, Serious and fatal Adverse Event (SAE), graded using NCI CTCAE Version 5.0.

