9.4.2 Safety Analyses

The safety endpoints will include:

- Incidence of DLTs
- Incidence of AEs and related AEs
- Incidence of grade 3 and grade 4 AEs
- Incidence of SAEs and death
- Laboratory values
- ECG/vital signs

The safety endpoints will be listed and/or summarized by dose cohort. No inferential statistical analyses will be performed.

The analyses of safety will be based on the frequency of adverse events and their severity for patients in each portion who received at least one dose of study treatment. Worst toxicity grades per patient will be tabulated for select adverse events and laboratory measurements by using NCI CTCAE criteria v5.0.

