## 10.6.2 Adverse Events

Analysis set: Safety

Note:

- If needed, adverse event data may be presented for all patients.
- The dose reduction information will be compiled using the treatment exposure page and AE page of eCRF through common AE number.

The frequency of adverse events (AEs) will be computed by counting each patient only once per MedDRA [Version 24.0] preferred term and according to the maximum NCI CTCAE v.5.0 grade attained by the patient over the specified period. The percentage of patients with an event will be calculated using the number of patients in the safety analysis set as the denominator.

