### **Standard Summaries of Adverse Events**

Treatment Emergent Adverse Events (TEAEs) are those that start on or after the date of first dose of study medication.

An overall summary of TEAEs (number and percentage of patients along with the number of events) will be presented with the following:

- Any TEAE
- Treatment Related TEAEs
- Serious TEAEs
- Treatment Related Serious TEAEs
- Grade 3 or 4 TEAEs
- Treatment Related Grade 3 or 4 TEAEs
- DLTs (Note: Applicable for dose escalation phase only)
- TEAEs leading to drug interruptions
- Related TEAEs leading to drug interruptions
- Serious TEAEs leading to drug interruptions
- Treatment Related Serious TEAEs leading to drug interruptions
- TEAEs leading to dose reduction
- Related TEAEs leading to dose reduction
- Serious TEAEs leading to dose reduction
- Treatment Related Serious TEAEs leading to dose reductions

- TEAEs leading to drug withdrawn permanently
- Treatment Related TEAEs leading to drug withdrawn permanently
- Serious TEAEs leading to drug withdrawn permanently
- Treatment Related Serious TEAEs leading to drug withdrawn permanently
- Fatal TEAEs
- Treatment Related Fatal TEAEs
- Protocol-Defined Adverse Events of Special Interest:
  - Pregnancy, abortion, birth defects/congenital anomalies
  - Overdose

Summaries showing the number of patients (n, %) along with number of events by SOC and PT will be provided for the following:

- DLTs (Note: Applicable for dose escalation phase only)
- TEAEs
- Related TEAEs
- Non-TEAEs
- Grade 3, 4 and 5 TEAEs
- Related Grade 3, 4 and 5 TEAEs
- Treatment-Emergent SAEs
- Related Treatment –Emergent SAEs
- TEAE with maximum CTCAE grade
- Treatment-Related TEAEs with maximum CTCAE grade per suspected drug(s) [Tenalisisib, Romidepsin or Combination]
- Deaths
- TEAEs leading to drug interruptions
- TEAEs leading to dose reduction
- TEAE leading to drug withdrawn permanently

The adverse events data will also be listed for individual patients.

- Any non-TEAE
- TEAEs
- Related TEAEs
- SAEs
- Treatment Emergent Grade 3, 4 and 5 AEs
- Treatment Related Grade 3, 4 and 5 AEs
- Treatment Related SAEs
- TEAEs leading to drug interruptions
- TEAEs leading to dose reduction
- TEAE leading to drug withdrawn permanently

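### Protocol 7.4.3 gives opposite instructions for an isolated Grade 3 or 4 laboratory abnormality judged not clinically significant, and Grade 3/4 AEs are part of the primary endpoint

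*Protocol*

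**What the plan says.** Protocol 7.4.3 opens with the rule on which laboratory values become AEs: "Any grade 3 or 4 laboratory abnormalities or any clinically significant grade 1 or 2 hematology or biochemistry laboratory value(s) should be recorded". The sentence after it reads: "Isolated laboratory abnormality without clinical significance should not be captured as AE if confirmed by the investigator". Two further sentences deal with values that come with signs or symptoms, where the sign or symptom becomes the AE, and with values that belong to a disease or syndrome, where the diagnosis alone is needed.

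The primary endpoint in Protocol 3.1.1, repeated in SAP 4.1, is "Adverse Event (AE), Grade 3/ 4 AEs, Serious and fatal Adverse Event (SAE), graded using NCI CTCAE Version 5.0". Protocol 9.4.2 lists "Incidence of grade 3 and grade 4 AEs" among the safety endpoints. It also plans a tabulation of worst CTCAE grade per patient for selected AEs and laboratory measurements.

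SAP 10.6.2 works from AE records: "The frequency of adverse events (AEs) will be computed by counting each patient only once per MedDRA [Version 24.0] preferred term", at the maximum CTCAE grade. Its overall summary includes Grade 3 or 4 TEAEs and "Treatment Related Grade 3 or 4 TEAEs". SAP 10.6.3 plans descriptive statistics of absolute laboratory values by visit, a full listing and a separate listing of abnormal values. It names no table by CTCAE grade.

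**The concern.** The two opening sentences of 7.4.3 meet at one kind of case: a Grade 3 or 4 laboratory value that stands alone and that the investigator confirms is not clinically significant. One sentence requires an AE record and the other forbids it. The study is open-label, has no control arm and runs at about 15 centers, so different sites can reasonably settle the conflict differently.

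The Grade 3/4 AE count would then depend partly on which sentence a site followed. The second sentence can only remove records, so where it is followed the effect is towards fewer Grade 3/4 events. The count is part of the primary endpoint, and there is no concurrent arm in which the same recording habit would show.

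**Working it through.** The plan states no figure for this point, so the check sets the sentences side by side and follows them to the tables.

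**1. What each sentence requires for an isolated value**

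| Isolated laboratory value | First sentence | Second sentence |
|---|---|---|
| Grade 1–2, clinically significant | record | does not apply |
| Grade 1–2, not significant | recording not required | do not record |
| Grade 3–4, clinically significant | record | does not apply |
| Grade 3–4, not significant, confirmed by investigator | record | do not record |

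Only the last row conflicts. Values with symptoms or an underlying diagnosis are covered by the later sentences of 7.4.3 and are outside the problem.

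**2. Can either reading remove the conflict?** If the second sentence is confined to Grade 1–2, it adds almost nothing, because the first sentence already leaves non-significant Grade 1–2 values out; only the investigator's confirmation is new. The limit is also not written. If the second sentence is an exception for all grades, the unconditional rule for Grade 3 or 4 is untrue as it stands. Neither document gives an order of precedence.

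**3. Does it reach the primary endpoint?** Yes. Grade 3/4 AEs are named in the endpoint, and the SAP counts them from AE records. A value that is not entered as an AE is absent from every Grade 3/4 TEAE table and remains only in the laboratory listings and per-visit summaries.

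**4. Which values are exposed?** Mainly those with no dose action attached, or judged unrelated to study drug. For Grade 3 neutropenia and thrombocytopenia attributed to Tenalisib, the action in Table 7 begins by keeping the dose level. Lymphopenia and anemia are listed as Romidepsin effects in Protocol 3.4.5.2, but neither Table 7 nor 7.7.3.1 names them. This describes where the recording gap lies and is no comment on the dose rules.

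**5. Is there a scale?** Protocol 1.1.2 lists treatment-related Grade ≥3 events for RP6530-1401 by term:

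- All listed: 12 + 4 + 2 + 1 + 1 + 1 + 1 + 1 + 1 + 1 = 25.
- Laboratory terms: AST/ALT 12 + hypophosphatemia 2 + neutropenia 1 + INR 1 = 16, and 16/25 = 64%.

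This 64% is not an estimate of loss. One raised INR also appears among the treatment-related SAEs, so that event was apparently serious: 16 − 1 = 15. AST/ALT elevation at Grade ≥3 triggers withholding under Table 8 of this protocol: 15 − 12 = 3. Hypophosphatemia would fall under the Table 8 row for other Grade 3/4 non-hematologic toxicity, which also requires a hold: 3 − 2 = 1. That leaves one neutropenia, free of a hold under Table 7 only if it was Grade 3.

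The list cannot size the effect in the other direction either. It covers related events only, comes from Tenalisib without Romidepsin, and does not say which events were isolated.

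**The case against.** The strongest reply is that other rules narrow the gap.

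- **Dose rules.** A value that obliges the investigator to hold or reduce a drug is hard to call insignificant. Table 8 does this for Grade ≥3 AST/ALT and other Grade 3/4 non-hematologic toxicity, and 7.7.3.1 delays Romidepsin for Grade 3 or 4 neutropenia or thrombocytopenia attributed to it. SAP 10.6.2 links dose reductions to AEs through a common AE number, which presupposes an AE record. This stands, and it is why the point is confined to values without dose action or judged unrelated.
- **Other views of the data.** Laboratory values are a safety endpoint in their own right, abnormal values are listed, and DLTs have their own grade and duration criteria. This stands in part. A listing does not correct a Grade 3/4 AE table. The DLT criteria exclude some transient severe values, such as Grade ≥3 AST/ALT that falls to Grade 2 or lower within 14 days. The graded laboratory table promised in Protocol 9.4.2 does not appear in SAP 10.6.3.
- **No inference.** Safety is descriptive only, so no test or error rate is affected. True, but the descriptive count is the primary result.

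A reader might infer that an asymptomatic ALT of 8 × ULN must go unrecorded. The documents do not support that: Table 8 withholds Tenalisib above 5 × ULN, and absence of symptoms is not the same as absence of clinical significance.

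**Conclusion.** The contradiction is real and rests on the text alone: for an isolated Grade 3 or 4 laboratory abnormality judged not clinically significant, 7.4.3 both requires and forbids an AE record. It reaches the primary endpoint, and its direction is towards fewer recorded Grade 3/4 events at sites that follow the second sentence.

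Its size in this trial cannot be derived from the documents. A reader might infer that, if a quarter to half of the 16 laboratory events were dropped, 4 to 8 of 25 (16% to 32%) would be missing. Neither document gives any omission rate, and the 16 include events that dose rules or seriousness would bring into the record. A reader might also infer that the combination will be shown as safer than it is. That would require knowing how sites acted and how many exposed values occurred, and the plan tells us neither. What can be said is that the plan permits under-recording of a limited class of Grade 3/4 events and names no graded laboratory table that would reveal it. A short correction is worth making.

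**What to change.** In Protocol 7.4.3, restrict the second sentence to Grade 1 or 2 abnormalities and add that an isolated Grade 3 or 4 laboratory abnormality is recorded as an AE. The word isolated matters: an unqualified rule for all Grade 3 or 4 values would collide with the later sentences on symptoms and diagnoses, which should stay unchanged. Put the same rule in the eCRF completion guideline.

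In SAP 10.6.3, add the worst-CTCAE-grade laboratory table foreseen in Protocol 9.4.2. Before database lock, reconcile Grade 3–4 laboratory values against AE records. That step also helps if sites have already recorded under different readings.

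The cost is one edited passage, one table and a reconciliation check, with slightly more AE records and a slightly higher reported Grade 3/4 rate. No treatment rule changes.

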### 10.6.3 Clinical Laboratory Tests

Analysis Set: Safety

Laboratory data will be presented per cycle for each phase.

Baseline will be defined in each phase of the study. The baseline measurement will be the last pre-treatment measurement taken on or before Cycle1 Day1 in respective phase. For Dose Escalation phase, the baseline will be the last pre-treatment measurement taken on or before the Cycle 1 Day 1 dose for Romidepsin, and for Dose Expansion phase, the baseline will be the last pre-treatment measurement taken on or before Cycle 1 Day 1 dose of Romidepsin or Tenalisib whichever is earlier.

Absolute values of laboratory parameters will be presented at each visit using descriptive statistics (n, mean, median, standard deviation, minimum and maximum values).

The laboratory data will also be listed.

A separate listing of patients with abnormal laboratory test values will also be presented.

Hematology	Chemistry Panel I	Chemistry Panel II	Urinalysis	Other
Hematocrit	Total bilirubin	Blood glucose	Blood	PT
Hemoglobin	Alkaline phosphatase (ALP)	Urea or blood urea nitrogen	Glucose	INR
CBC with differentials	Alanine aminotransferase (ALT)	Albumin	Protein	
Platelet count	Aspartate aminotransferase (AST)	Total protein	Specific gravity	
WBC (Total and differentials)	Lactate dehydrogenase (LDH)	Total Cholesterol	Microscopic exam	
Red blood cell count	Gamma-glutamyl transferase	Triglyceride (TG)		
Absolute neutrophil count	Sodium	LDL		
Absolute lymphocyte count	Potassium	HDL		
	Calcium	TSH		
	Phosphorous	T3 (Total or Free)		
	Bicarbonate or Carbon Dioxide (CO2)	T4 (free)		
	Chloride	Creatinine		
	Magnesium			

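### Protocol 7.4.3 does not settle how a symptomatic Grade 3 or 4 laboratory abnormality is recorded, so some may be missing from the Grade 3/4 AE tables

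*Protocol*

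**What the plan says.** Protocol 7.4.3 gives four rules in sequence.

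1. "Any grade 3 or 4 laboratory abnormalities" must be entered as AEs, and so must clinically significant Grade 1 or 2 values. There is no exception for abnormalities that come with symptoms.
2. "Isolated laboratory abnormality without clinical significance should not be captured as AE if confirmed by the investigator". This concerns isolated findings.
3. "If an abnormal laboratory value or vital sign is associated with clinical signs and/or symptoms, the sign or symptom should be reported as an AE". On the value itself, the rule is that "the associated laboratory value or vital sign should be considered additional information that must be collected on the relevant eCRF".
4. If the abnormality is a sign of a disease or syndrome, the diagnosis is the only entry needed.

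The primary endpoint (protocol 3.1.1, repeated in SAP 4.1) is "Adverse Event (AE), Grade 3/ 4 AEs, Serious and fatal Adverse Event (SAE), graded using NCI CTCAE Version 5.0". SAP 10.6.2 counts each patient once per preferred term at the maximum CTCAE grade, and its Grade 3/4 summaries are built from recorded treatment-emergent AEs.

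For laboratory data, protocol 9.4.2 plans a tabulation of each patient's worst CTCAE grade for selected AEs and laboratory measurements. SAP 10.6.3 says instead: "Absolute values of laboratory parameters will be presented at each visit using descriptive statistics". It adds a listing of the data and a separate listing of abnormal values, but no summary by CTCAE grade.

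**The concern.** Rule 1 and rules 3 and 4 give different instructions for the same case. Take a Grade 3 ALT rise in a patient who also has Grade 1 fatigue attributed to it. Under rule 1 there is a Grade 3 AE. Under rule 3 the AE is the fatigue, and the ALT value is supporting data. No text ranks the rules, and none says that the symptom or diagnosis takes the laboratory grade.

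The grade matters because Grade 3/4 AEs are part of the primary endpoint and the AE tables use only what is entered as an AE. The toxicities affected are ones the protocol expects: ALT/AST elevation and neutropenia with Tenalisib (3.4.5.1), and cytopenias with Romidepsin (3.4.5.2). With about 15 centers and 12 patients per expansion group, differences between sites in recording would not average out.

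**Working it through.** The plan states no figure that could be reproduced here. The check is mainly a comparison of texts, followed by an illustration of the possible size.

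**Step 1. Which rule governs?** Rule 1 covers any Grade 3 or 4 laboratory abnormality. Rule 3 covers any abnormal value with signs or symptoms, at any grade. Both apply to a symptomatic Grade 3 or 4 value. Rule 3 does not forbid a second AE record, so a site can satisfy both rules. But rule 3 contrasts what is reported as an AE with what "should be considered additional information that must be collected on the relevant eCRF", and it is the more specific rule for symptomatic cases. A site that enters only the symptom is therefore also following the text. Rule 4 is explicit that one entry is enough.

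**Step 2. Does another section settle the grade?** Protocol 7.4.2 says to use the highest grade, but only for one persistent AE whose severity changes. It does not address a laboratory value behind a symptom. Protocol 7.4.1 prefers a diagnosis to separate signs, without a grading rule.

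**Step 3. Is the grade recovered elsewhere?** The values are collected and listed, so no raw data are lost. The protocol 9.4.2 tabulation would show laboratory grades whatever AE term was chosen. SAP 10.6.3 does not include it, and SAP section 2 says that the SAP may modify the protocol's plans. As the SAP stands, no summary table shows the laboratory grade.

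**Step 4. How much of the Grade 3 or higher experience could be affected?** Protocol 1.1.2 lists treatment-related Grade 3 or higher toxicity in the earlier Tenalisib monotherapy trial (RP6530-1401).

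- Laboratory findings: AST/ALT 12 + hypophosphatemia 2 + neutropenia 1 + INR 1 = 16.
- Other: rash 4 + sepsis 1 + pyrexia 1 + diplopia 1 + drug reaction 1 + bacteremia 1 = 9.
- Laboratory share: 16 / (16 + 9) = 16/25 = 64%.

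Let s be the share of such laboratory events that carry a symptom of lower grade. The documents do not give s. The largest proportional fall in the Grade 3 or higher count is 0.64 × s: 6.4% at s = 10%, 16% at s = 25% and 32% at s = 50%. This bound is reached only if every such event is entered under rule 3 or 4 alone.

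**Step 5. In patients.** Read the 12 AST/ALT elevations as 12 of the 58 treated patients (an assumption), so p = 12/58 = 20.7%. Let s now be the share recorded only as a lower-grade symptom. For the 24 expansion patients, the expected number tabulated is 24 × p × (1 − s), and the chance that at least one is lost is 1 − (1 − p × s)^24.

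| s | Expected in Grade 3+ table | Rate | Chance of losing at least one |
|---|---|---|---|
| 0 | 4.97 | 20.7% | 0% |
| 10% | 4.47 | 18.6% | 39.5% |
| 25% | 3.72 | 15.5% | 72.0% |
| 50% | 2.48 | 10.3% | 92.7% |

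The first row is the result if rule 1 is always applied. The others show what could happen, not what sites will do.

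**The case against.** A reader might infer that 7.4.3 replaces the laboratory abnormality by the symptom alone, so that adding a symptom always lowers the recorded grade and the primary count is biased downward. The documents do not support that. Rule 1 has no exception for symptomatic cases, both entries can be made, and rule 3 does not say that the symptom is the only AE. The symptom may also have an equal or higher grade.

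A reader might also infer that nothing in the plan could recover the grade. Protocol 9.4.2 does plan a worst-grade laboratory tabulation, and abnormal values are listed. The gap is that the SAP does not carry the tabulation over.

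Other points also stand:

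- The protocol's own names for conditions are graded by laboratory value: neutropenia and thrombocytopenia in 7.6.1 and Table 7, transaminitis in Table 8. A low platelet count with bruising can be recorded as thrombocytopenia at its laboratory grade. This reduces the concern for named cytopenias. It does not cover a value whose symptom is entered under rule 3.
- The hematological and ALT/AST criteria for dose-limiting toxicity in 7.6 use toxicity grade and resolution directly, so they do not depend on the AE term chosen here.
- Safety is descriptive (9.4.2), so no test or error rate is affected.
- One patient is 1/12 = 8.3 percentage points of a group. But a patient leaves the overall Grade 3/4 count only if no other Grade 3/4 AE is recorded for that patient.

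None of this says which rule prevails.

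**Conclusion.** The point holds as an internal inconsistency that may lower the Grade 3/4 AE counts, not as a certain bias. An event is missed only if the site follows rule 3 or 4 without rule 1, and the symptom or diagnosis is graded lower than the laboratory value. How often both occur is unknown.

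The 0.64 × s figure is an upper bound for an assumed s. It rests on the monotherapy mix of toxicities carrying over to the combination, and on each n in protocol 1.1.2 counting one occurrence. The patient illustration also reads n as patients. The loss would be in the summary tables, not in the database. It is still worth correcting, because these tables report part of the primary endpoint, the groups are small and the correction is cheap.

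**What to change.** In protocol 7.4.3 and the eCRF completion instructions, state that rule 1 applies whether or not symptoms are present: a Grade 3 or 4 laboratory abnormality is recorded with its own CTCAE grade in addition to any symptom. Where only a diagnosis is recorded, it carries the higher of the laboratory and clinical grades.

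In SAP 10.6.3, add the worst-CTCAE-grade-per-patient laboratory table that protocol 9.4.2 already plans, and name the parameters it covers.

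The protocol change is a short clarification. The SAP table uses data already collected. The one drawback is that a single episode may give two AE records, which raises event counts. Patient counts per preferred term stay valid, because SAP 10.6.2 counts each patient once per term.
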